3.4. Selection and withdrawal of participants

3.4.1 Recruitment

Study Setting

Patients will be identified from General Practices (GP) acting as Patient Identification centres (PIC) and then clinically assessed at their local secondary care research centre site (all sited in rheumatology services with strong axSpA expertise). GP practices surrounding each research centre will identify patients presenting with CBP by Systemized Nomenclature of Medicine (SNOMED) code or prior identification as a back pain consultation. General Practice Clinicians (GPCs) responsible for evaluating patients with back pain will reflect the present clinical diversity of health professional expertise assessing this patient group and may include general practitioners, physician associates, first contact physiotherapists and practice nurses.

Participant Identification, screening, and recruitment

Participants may be approached by a variety of methods:

1) Pop-up method

Patient with back pain consults their general practice, dependent on the availability of staff at the GP practice, patients may be given a miniaturised copy of the study poster to prompt discussion during their consultation.

GPC enters 'back pain' SNOMED code, triggering patient eligibility screen template (pop-up) in electronic health record (EHR) if patient is aged between 16-50 years.

GPCs will assess for suspected red flag exclusion criteria in potential participants (see 3.4.2 Eligibility criteria). If a patient is potentially eligible and the GPC deems them suitable for the study, they will briefly introduce the study and ask the patient whether they would be willing to receive an SMS invitation to the study. The GPC will complete a simple and brief

Page 20 of 53

IDEAL BACKPACS Protocol Final Version 1.1 date 09-Oct-l2024

electronic pop-up to confirm the patient has current back pain and more than 3 consecutive months of chronic back pain in the last 12 months, absence of red flags and verbal agreement for an SMS invite to be sent. If the patient is not eligible, or not interested in being contacted about the study, the GPC will indicate this within the pop-up. If a potential participant fails screening, and then later presents with > 3 months back pain, they can be re-screened for eligibility at the GP primary care assessment stage.

If the patient agrees to be contacted, an SMS text message invite will be sent to them by the GP practice, containing a link for the online electronic Participant Information Sheet (ePIS), and a summary of the consent clauses which can be downloaded by the potential participant if they wish. Participant information will be provided in a variety of engageable formats (may include infographics, videos, and language translation). An additional link which will direct patients to the REDCap study database, will ask whether they accept or decline the invitation to be contacted to hear more about the study. Those who decline will be advised to contact their GP if their symptoms persist. Those who accept will provide information in the REDCap database to include (but not limited to), full name, date of birth, GP surgery, contact telephone number, email address and need for a video call (if hearing impaired). Site specific reports will be generated containing the personal contact details of interested patients, these will be accessed by the local secondary care team to facilitate a research eligibility telephone call, or video call.

Regular reports may be generated within the GP systems containing information on patients approached and considered, and how many patients are deemed ineligible at the pop-up stage. These anonymous and aggregated reports will be shared with the coordinating centre as means of tracking screening/enrolment.

For patients that accept the invitation to join the study, the local secondary care research team will follow-up with a telephone call (or video call, if the patient requires this e.g. is deaf or hearing impaired) to confirm receipt of the study information, provide an additional verbal explanation of the study, answer any questions, and, if interested, confirm eligibility. Potential participants who are interested and confirmed eligible during the telephone call will be provided with a personal link to the online electronic Informed Consent Form (eICF) (see section 3.4.5), enabling them to review the requirements of the study and provide written informed consent (as detailed below).

It will be explained to the potential participant that entry into the study is entirely voluntary and that their treatment and care will not be affected by their decision. It will also be explained that they can withdraw at any time, but attempts will be made to avoid this occurrence. In the event of their withdrawal, it will be explained that their data collected so far cannot be erased and we will seek consent to use the data in the final analyses where appropriate.

For patients with poor IT/literacy skills we will develop animated videos describing the study to improve accessibility and recruitment for patients with first language other than English, and those underserved groups.

2) Retrospective search of electronic health record

Recruitment will be regularly assessed by the Programme Management Group (PMG), if recruitment is not sufficient using method 1, potentially eligible patients will be identified by a search of the GP clinical system for patients who have consulted with their GP previously (up to 12 months) using pre-specified back pain SNOMED codes. Where available, SNOMED codes for exclusion criteria will be used to remove patients not eligible for the study. GPC clinical staff may then review the generated list of patients for anyone inappropriate to invite into the study.

Page 21 of 53 IDEAL BACKPACS Protocol Final Version 1.1 date 09-Oct-l2024

A letter and/or SMS message will be sent to the identified list of patients to invite them to take part in the study. This will include a link to or copy of the PIS. They will also be provided with a link which will direct them to the REDCap study database and will ask whether they accept or decline the invitation to be contacted to hear more about the study. Patients that express an interest in the study will then follow the processes as described in method 1.

Managing patient flow from primary to secondary care

The pop-up can be switched on/off at any time, either through the local NIHR Research Delivery Network (RDN, formally known as Clinical Research Network; CRN) or GP practices. If needed, we will limit the number of active recruiting GPs we have at one time, to enable staggering of secondary care appointments. Current waiting lists at each trust involved in the study can vary. It is important that we do not overwhelm capacity within the research clinics to ensure that patients referred into the study by their general practice are seen and assessed in a timely fashion.

Posters advertising the study may be displayed in participating GP practices.

3.4.2 Eligibility criteria

Inclusion criteria

- Aged 16-50 years with onset of chronic back (cervical/thoracic/lumbar) pain before 45 years.
- Current back pain and at least 3 consecutive months of chronic back pain in the last 12 months.
- Ability to provide written/electronic informed consent.
- Willingness and ability to undergo all study assessments (i.e. clinical examination, X-ray, MRI, blood sample collection).

Exclusion criteria

- Existing diagnosis of axSpA.
- Existing diagnosis of inflammatory arthritis.
- GPC deems unsuitable.
- Radiation of leg pain below the knee (i.e. neuralgia/sciatica)
- Contraindications to MRI, e.g.:
 - o Pacemaker
 - Other ferrous metal in situ
 - Pregnancy (0-12 months post-partum)
 - Claustrophobia

Suspected red flags in the history or clinical examination that may indicate further investigation or referral for possible serious underlying pathology:

- Cauda Equina Syndrome
- Spinal Fracture
- Cancer
- Bone/disc infection

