2.3 Secondary Objectives

- Determine the most clinically effective ('superior') referral strategy by comparative
 analysis of the four pre-existing candidate strategies [the Baraliakos [9], modified
 Braun [45], ASAS [44] and CaFaSpA [15]) and the BACKPACS model. The study
 team anticipate that this will result in either the BACKPACS or Baraliakos strategy
 going forward as the 'pop up' in a separate implementation study, IDEALDIRECTED.
- To compare the acceptability and clinical effectiveness of the BACKPACS and Baraliakos referral strategy.
- Evaluate the NASS patient screening questionnaire to determine whether patient self-assessment prior has the potential to reduce delays in diagnosis.
- Estimate of prevalence of axSpA in UK primary care CBP population.
- Evaluate the individual potential screening variables.
- To assess the cost-effectiveness of different axSpA referral strategies, comparing strategies with current care and a comparison between strategies in a fully incremental analysis, applying the rules of simple and extended dominance.

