3.1.3 Index tests

Index tests are the BACKPACS model (to be developed within this study) in addition to existing referral strategies described in Table 3.

Page 17 of 53 IDEAL BACKPACS Protocol Final Version 1.1 date 09-Oct-l2024

Table 3: Index tests

Index tests	Assessment
The Baraliakos strategy [9]	Assesses 3 clinical variables. If 2 or 3 of these variables are present (or a 'second step' HLA-B27 test is positive) then secondary care referral is suggested:
	 improvement in pain with NSAIDs after 48 hours raised CRP (blood test)
	• early morning stiffness (≥ 30minutes)
	This strategy requires follow up after the initial primary care clinic appointment.
The Modified Braun strategy [45]	Assesses 10 clinical variables and if at least 4 of these 10 variables are present then secondary care referral is suggested:
	 low back pain that started before the age of 35 years waking during the second half of the night because of symptoms buttock pain
	 improvement with movement improvement with non-steroidal anti-inflammatory drugs (NSAIDs)
	 a first-degree relative with spondyloarthritis, current/past arthritis,
	• current/past enthesitis
	current/past psoriasisHLA-B27 genetic test
The 'Assessment of SpondyloArthritis international Society (ASAS) strategy [44]	Patients with chronic backpain (≥ 3 months) with onset before 45 years, should be referred if at least one clinical variable is present:
1	Inflammatory backpain HLA-B27 positive
	 Sacroiliitis on imaging, if available (x-ray or MRI) Peripheral manifestations (arthritis, enthesitis and/or dactylitis)
	 Extra-articular manifestations (psoriasis, inflammatory bowel disease and/or uveitis) Family history for spondyloarthritis
	Good response to NSAIDS Acute elevated phase reactants (c-reactive protein or erythrocyte sedimentation rate)
The CaFaSpA referral strategy[15]	Easy to use and was developed in a primary care setting but was not adopted by NICE spondyloarthritis clinical guideline[3], as the study cohort reported a much lower than expected prevalence of HLA-B27 positive individuals. The explanation for this may be related to the study having a lengthy retrospective recruitment time

Page 18 of 53 IDEAL BACKPACS Protocol Final Version 1.1 date 09-Oct-l2024

for individuals with CBP (median 10 years), whilst
excluding patients diagnosed with axSpA during this
period; many of the excluded individuals with axSpA
would have been HLA-B27 positive. This approach

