		and Leeds Enthesitis Index (LEI)
		16 sites assessed in total: the greater trochanter, quadriceps tendon insertion into the patella, patellar ligament insertion into the patella and tibial tuberosity, Achilles tendon insertion, plantar fascia insertion, medial and lateral epicondyles, and the supraspinatus insertion. Presence or absence of tenderness; max
		score = 16
Mobility	Bath Ankylosing Spondylitis Metrology Index (BASMI)	Index comprising 5 measures of spinal and hip mobility
Personal history	 a. Onset of chronic back pain symptoms b. Dactylitis c. Enthesitis d. Skin/nail psoriasis, e. Colitis f. Uveitis g. Anterior chest pain 	Self-reported, current and previous
Family history	Presence in first degree or second- degree relatives* of any of the following: a. Skin/nail psoriasis b. Colitis c. Uveitis, d. axSpA, e. Reactive arthritis, f. PsA	Self-reported (yes/no) and number of relatives affected
Response to NSAIDs	Only if NSAID response is not completely clear. At least one week at max tolerated dose. (If NSAID response if not completely clear) for individuals with no contraindications, min 7-day course of full dose NSAIDs (with telephone evaluation of NSAID response from research team at 1 week)	Self-reported (yes/no)

Page 30 of 53 IDEAL BACKPACS Protocol Final Version 1.1 date 09-Oct-2024

Blood tests	Blood tests			
Diagnostic laboratory tests	HLA-B27	Positive testing according to standard laboratory techniques.		
	CRP	C-reactive protein above upper normal limit in the presence of back pain, after exclusion of other causes for elevated CRP concentration.		
Imaging				
x-ray	Conventional SIJ plain x-rays	Modified New York criteria for each SIJ		
MRI	SIJ and whole spine (30 min scan) arranged within 4 weeks** of clinical assessment.	 (i) Description of oedema and structural features (fat metaplasia, erosions, ankylosis) in SIJs – yes/no for each. Interpretation according to ASAS specifications (bone marrow oedema in typical location 'highly suggestive' of axSpA) - yes/no for MRI positivity (ii) Are there unequivocal features of spinal inflammation? (yes/no) (iii) Overall impression across x-ray and MRI – (a) normal (b) equivocal (c) axSpA (d) other 		

^{*}First degree relative includes an individual's parents, siblings and children. Second degree relative includes grandparent, grandchild, half siblings, aunt/uncle and niece/nephew. **where possible, waiting times may vary between sites.

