86. Braun V, Clarke V: Using thematic analysis in psychology. Qualitative Research in Psychology

2006, 3(2):77-101.

- 87. Braun VC, V.: Thematic analysis. Research methods in social sciences: An A-Z of key concepts: Open University Press.; 2021.
- 88. Creswell JW, Miller DL: Determining Validity in Qualitative Inquiry. Theory Into Practice 2000, 39(3):124-130.

Appendices

Appendix 1: Specification of the variables used for the ASAS-Criteria for classification of Axial Spondylarthritis

Clinical Feature of axSpA	Definition
Inflammatory back pain (IBP)	IBP according to experts: 4 out of 5 of the
, , , , , , , , , , , , , , , , , , ,	following parameters present:
	1. Age at onset < 40 years
	2. Insidious onset
	3. Improvement with exercise
	4. No improvement with rest
	5. Pain at night (with improvement upon getting up)
Good response to NSAIDs	24-48 hours after a full dose of a non-steroidal
	anti-inflammatory drug (NSAID) the back pain is
	not present any more or much better.
	(the clinical co-applicants on the PGfAR IDEAL
	grant have concluded that response after one
	week would be more appropriate)
Arthritis	Past or present active synovitis diagnosed by a physician.
Dactylitis	Past or present dactylitis diagnosed by a
	physician.
Enthesitis	Heel enthesitis: past or present spontaneous
	pain or tenderness at examination of the site of
	the insertion of the Achilles tendon or plantar
	fascia at the calcaneus.
	(a broader evaluation of enthesitis is also being
	evaluated for the IDEAL study cohort)
Psoriasis	Past or present psoriasis diagnosed by a
	clinician.
Inflammatory bowel disease (IBD)	Past or present Crohn's disease or ulcerative
	colitis diagnosed by a physician.
Uveitis anterior	Past or present uveitis anterior, confirmed by an
	ophthalmologist.
Family history	Presence in first-degree or second-degree
	relatives of any of the following:
	a. Ankylosing spondylitis
	b. Psoriasis
	c. Uveitis
	d. Reactive arthritis
	e. IBD
HLA-B27	Positive testing according to standard laboratory
	techniques.
Elevated CRP	C-reactive protein above upper normal limit in
	the presence of back pain, after exclusion of
	other causes for elevated CRP concentration.

Page 53 of 53 IDEAL BACKPACS Protocol Final Version 1.1 date 09-Oct-2024

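### Past arthritis is scored by modified Braun and by the ASAS classification but is not collected in Table 6, and the arthritis exclusion does not say whether a resolved episode counts

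*Protocol*

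**What the plan says.** **Who is excluded.** Section 3.4.2 of the protocol (and the synopsis) excludes an "Existing diagnosis of inflammatory arthritis", listed next to the exclusion of known axSpA. A resolved past episode is not mentioned.

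**What the rules score.**
- Modified Braun (section 3.1.3, Table 3) has an item for "current/past arthritis". Its threshold is "if at least 4 of these 10 variables are present then secondary care referral is suggested".
- The ASAS referral strategy (same table) has one composite item, "Peripheral manifestations (arthritis, enthesitis and/or dactylitis)", and a patient "should be referred if at least one clinical variable is present".
- Baraliakos has no arthritis item. Table 3 does not list the CaFaSpA items.
- Appendix 1 specifies the variables of the ASAS classification, which section 3.1.2 makes the secondary reference standard. It defines arthritis as "Past or present active synovitis diagnosed by a physician".

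**What is collected.** Table 6 (section 4.1.4) lists a 66/68 swollen and tender joint count. Its personal history, asked as current and previous, covers back pain onset, dactylitis, enthesitis, psoriasis, colitis, uveitis and "Anterior chest pain". Past arthritis is not on the list. The clinical features named for the participant questionnaire in section 4.1.3 are psoriasis and NSAID response.

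**What the data are for.** Section 2.3 plans a comparative "analysis of the four pre-existing candidate strategies" together with the BACKPACS model, and an evaluation of the individual screening variables.

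**The concern.** There are two linked gaps.

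First, an index test and the secondary reference standard each contain an item with a past component, and the plan lists no field for that component. Past dactylitis and past enthesitis are requested, so the missing arthritis question looks like an oversight. An analysis plan written later cannot recover a history that was never taken.

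Second, the exclusion has no single meaning for someone whose arthritis has resolved. Whether such a person is enrolled, and can contribute to the arthritis item at all, could depend on the recruitment route or the site.

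At stake are the faithful scoring of modified Braun, the faithful scoring of the secondary reference standard, and the evaluation of arthritis as a candidate variable. The primary reference standard (the rheumatologist's diagnosis) and the scoring of Baraliakos do not depend on this item.

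**Working it through.** **1. Definitions against data.**

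| Item | Defined as | Current part collected? | Past part collected? |
|---|---|---|---|
| Modified Braun arthritis (Table 3) | current or past | yes, joint count | not listed |
| ASAS classification arthritis (Appendix 1) | past or present, physician-diagnosed | yes, joint count | not listed |
| ASAS referral peripheral item (Table 3) | arthritis, enthesitis and/or dactylitis; timing not stated | yes | dactylitis and enthesitis yes; arthritis not listed |

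The first two rows cannot be completed as defined.

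**2. Whom it affects under modified Braun.** With a threshold of 4 of 10, an unknown arthritis item changes the result only if exactly 3 of the other 9 items are positive. With 4 or more the patient is positive anyway; with 2 or fewer, negative anyway. Anyone with arthritis at the joint count is already scored. Section 5.3 restricts the primary analysis to participants whose index test and reference standard can be determined. Those at exactly 3 would therefore be either undetermined or scored as if they had no past arthritis.

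**3. Upper-end illustration of size.** The documents give no frequency for the arthritis item, so the following are assumptions: items are independent, the other nine share a common probability p, and the arthritis item is positive in a share r. Then

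P(rule positive) = P(at least 4 of 9) + r × P(exactly 3 of 9).

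Solve p to match Table 1 (sensitivity 0.86; false-positive rate 1 − 0.73 = 0.27), then set the item to zero.

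| Group | r | P(exactly 3 of 9) | Positive with item | Positive without item |
|---|---|---|---|---|
| axSpA | 10% | 0.107 | 0.86 | 0.849 |
| axSpA | 20% | 0.114 | 0.86 | 0.837 |
| axSpA | 30% | 0.122 | 0.86 | 0.823 |
| no axSpA | 2% | 0.266 | 0.27 | 0.265 |
| no axSpA | 5% | 0.264 | 0.27 | 0.257 |
| no axSpA | 10% | 0.262 | 0.27 | 0.244 |

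Sensitivity falls by 1.1 to 3.7 points and specificity rises by 0.5 to 2.6 points. With 720 × 0.14 ≈ 101 cases, the sensitivity change is about 1 to 4 patients. One standard error is √(0.86 × 0.14 / 101) = 3.5 points. Setting the whole item to zero overstates the loss at each assumed r, because the joint count still captures current arthritis.

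**4. Direction.** The starting LR+ is 0.86 / 0.27 = 3.19. (Table 1 prints 2.10 for this rule; that difference is a separate matter and is not used here.) Combining the three sensitivities with the three false-positive rates gives LR+ from 0.823 / 0.265 = 3.11 to 0.849 / 0.244 = 3.48. It is above 3.19 in 7 of the 9 combinations.

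**5. Effect of the exclusion itself.** Suppose the exclusion removes a share a1 of cases and a0 of non-cases (assumed ranges 0–20% and 0–5%), and take the extreme case that all of them are rule-positive. Then sensitivity = (Se − a1)/(1 − a1) and specificity = Sp/(1 − a0).
- Modified Braun: sensitivity (0.86 − 0.10)/0.90 = 0.844 at a1 = 10% and (0.86 − 0.20)/0.80 = 0.825 at a1 = 20%. Specificity 0.73/0.95 = 0.768 at a0 = 5%. LR+ runs from 3.06 (a1 = 20%, a0 = 0) to 3.71 (a1 = 0, a0 = 5%).
- ASAS referral rule (Table 1: 1.00 and 0.16): sensitivity (1 − a1)/(1 − a1) = 1.00 throughout; specificity 0.16/0.95 = 0.168 at a0 = 5%.

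**6. Recruitment routes (section 3.4.1).** Method 2 uses SNOMED codes for exclusion criteria, where available, to remove patients before any invitation, so an old arthritis code can exclude someone. In method 1 the pop-up confirms pain duration, absence of red flags and agreement to a text message. The remaining eligibility is settled by the research team on the call. With no definition of existing, the same resolved episode could lead to removal by one route and enrolment by the other.

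**The case against.** A reader might infer that the exclusion handicaps modified Braun and the ASAS strategy by design and tilts the choice of the superior strategy towards Baraliakos. The documents do not support that.

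- The physician-diagnosis wording belongs to Appendix 1 and the classification criteria. Table 3 does not attach it to either referral rule, so the modified Braun item is not close to incompatible with eligibility.
- Undiagnosed current arthritis is still found at the joint count, and past joint symptoms that were never diagnosed do not breach 3.4.2.
- On Table 1 figures the ASAS referral rule loses no sensitivity. For modified Braun, a fall in sensitivity comes with a rise in specificity, and LR+ can move either way.
- It is not shown that Baraliakos is untouched. Removing people with known inflammatory arthritis could also remove patients positive on CRP, stiffness or NSAID response.
- The 5-point sensitivity gap between Baraliakos and modified Braun in Table 1 (0.91 against 0.86) comes from two different cohorts, so it is no yardstick for bias.
- Excluding known disease suits a study of undiagnosed back pain in primary care, and all strategies are compared in the same participants.
- Reporting item frequencies or an analysis without the arthritis item is ordinary SAP content.

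All of this stands. It does not answer the data-collection gap or the undefined term. A clinician might record past arthritis informally in a semi-structured visit, but Table 6 is described as a standardised proforma, and informal recording would not give consistent scoring.

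**Conclusion.** The point holds as a mismatch between what is scored and what is collected, together with an undefined exclusion term. As written, the modified Braun arthritis item and the Appendix 1 arthritis feature cannot be scored in full, and a resolved episode has no fixed eligibility status across the two recruitment routes.

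The likely effect is small: at most about 1 to 4 points of modified Braun sensitivity in the illustrations, with some gain in specificity. Those figures rest on assumed item frequencies, independence and Table 1 values from patients already referred to rheumatology. Neither the direction nor the size of any effect on the ranking can be derived from the documents. The exclusion itself is defensible; its consequence is that findings on the strategies and on arthritis as a variable apply to people without known inflammatory arthritis.

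The correction is worth making because it costs almost nothing and cannot be made once the visits have taken place.

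**What to change.** 1. Add past arthritis to the Table 6 personal history: self-reported, with a second tick for whether a physician diagnosed it. The first serves the modified Braun item and the second the Appendix 1 definition.
2. State in section 3.4.2 whether a resolved past episode is an existing diagnosis. Apply the same meaning to the SNOMED search in method 2 and to the eligibility call. Which way to define it is for the study team.
3. When the strategies are ranked and arthritis is evaluated as a variable, note that the results apply to people without known inflammatory arthritis.

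Cost: one CRF field, one clarifying sentence and one line of interpretation. No additional participants or visits are needed.
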